5.8 Analysis of Secondary Endpoints

Three risk groups will be formed, based on the tertiles of the CHARM risk score. We will provide univariate summaries of each of the secondary outcomes by CHARM score risk group for each endpoint. We will then compare the risk groups multivariate models developed for each outcome separately as detailed below. All the demographic and baseline characteristics described in section 5.6 above will be considered via stepwise variable selection for inclusion in the model. Assuming an overall type I error of 10%, a significance level of 1% will be used for all secondary analyses based on Bonferroni adjustment since we will be considering 10 endpoints between section 5.8.1 and 5.8.9. A sensitivity analyses will also be done base on the CHARM score as a quantitative measure rather than tertile groups.

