5.8.1 Overall Survival

Kaplan-Meier curves will be constructed to estimate overall survival probabilities. A multivariate Cox regression model for the risk of death will be developed to estimate hazard ratios for the CHARM risk groups after adjustment for baseline characteristics as described above.

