5.8.4 Admission to a Skilled Nursing Facility

Cumulative incidence of the time to the first facility admission will be described, along with the number of facility admissions per person years of follow up. Time to first admission will be modeled using Cox regression for the cause-specific hazard of admission, in order to compare hazard ratios between CHARM risk groups after adjustment for baseline characteristics. A multivariate proportional rates/means model⁶⁵ for the rate of facility admission accounting for multiple admissions will be estimated after adjustment for baseline characteristics, in order to estimate the relative intensities of facility admissions between the CHARM risk groups

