5.8.6 Health Related Quality of Life

Summary of health-related quality of life measures will be scored according to the recommendations of the developers; of primary interest for this study are the summary measures for depression, anxiety and physical function. For the descriptive analysis only, health-related QOL scores for survivors at specific time points will be summarized using means and standard deviations. Patterns of missing health-related QOL data will be examined using graphical techniques and logistic regression models. At each time point, the effect of baseline covariates including the composite health risk score on the health-related QOL outcomes conditional on being alive at that time point will be estimated using the inverse probability of censoring-weighted generalized estimating equations with independent working correlation model of Kurland and Heagerty.⁶⁴ Subjects who do not complete all baseline assessments will continue to be followed. Therefore, multiple imputation methods may also be used. These methods will provide adjusted comparisons of mean health-related QOL between CHARM risk groups at each time point conditional on being alive at that time point.

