5.8.7 Acute GVHD

Incidence of acute GVHD grade II-IV and grade III-IV up to 180 days will be estimated with 95% confidence intervals using the cumulative incidence estimate, treating death prior to acute

GVHD as a competing event. A multivariate Cox regression model for the cause-specific hazard of acute GVHD will be estimated after adjustment for baseline characteristics. The hazard ratios of the CHARM risks groups in predicting acute GVHD will be compared.

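### Testing every secondary analysis at 1% does not guarantee the stated 10% overall error, because section 5.8 names about 21 to 23 CHARM-group comparisons, not 10; the survival tests also reuse the deaths that built the score

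*Protocol*

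**What the plan says.** Protocol section 5.8 forms three groups from the tertiles of the CHARM score and compares them on each secondary outcome. It fixes the overall type I error at 10% and then says "a significance level of 1% will be used for all secondary analyses based on Bonferroni adjustment since we will be considering 10 endpoints". It places these endpoints in 5.8.1 to 5.8.9. The quantitative score is kept for a sensitivity analysis.

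Several subsections plan more than one comparison:

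- Section 5.8.6 promises "adjusted comparisons of mean health-related QOL between CHARM risk groups at each time point" and names three domains of primary interest.
- Section 5.8.3 has a time-to-event model for disability, and also the effect of risk group on the mean disability score at each time point.
- Section 5.8.4 models time to first admission, and adds a model "for the rate of facility admission accounting for multiple admissions will be estimated after adjustment for baseline characteristics".
- Section 5.8.7 covers "Incidence of acute GVHD grade II-IV and grade III-IV up to 180 days".

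For overall survival, section 5.8.1 will "estimate hazard ratios for the CHARM risk groups after adjustment for baseline characteristics as described above". Sections 5.5 and 5.7.1 say that CHARM is developed on the whole cohort, with non-relapse mortality (NRM) as the outcome. Section 3.2.1 counts death from any cause.

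**The concern.** The protocol makes a numerical promise about its error rate. That promise holds only if the number of tests run at 1% matches the divisor of 10 and each test really has a 1% level. Neither condition is met as written.

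The divisor counts endpoints, while the 1% level is applied to every secondary analysis. Section 5.8 names no key visit, key domain, joint test or testing order that would give one test per endpoint. In addition, survival after acute GVHD (5.8.10) is tested but lies outside the range the protocol cites.

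The survival tests have a further problem. The score is chosen to separate these subjects by NRM, and is then tested on an outcome that contains the same NRM deaths. The 632+ bootstrap in 5.7.2 is stated for prediction error and explained variation only, so it does not protect these tests.

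At stake are the error rate that would be reported with the results, and an overall survival association that is partly built in. Overall survival is the first secondary objective in section 2.2.3.

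**Working it through.** **The plan's own figure.** 0.10 / 10 = 0.01, so the arithmetic of the 1% level is right. Ten tests at 1% have a bound of 10 × 0.01 = 10%, and 1 − 0.99^10 = 9.6% if independent.

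**Count of CHARM-group comparisons**, taking one omnibus three-group test per model:

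| Section | Comparisons | Number |
|---|---|---|
| 5.8.1 | overall survival | 1 |
| 5.8.2 | frailty | 1 |
| 5.8.3 | time to disability; mean score at days 100, 180, 365 | 1 + 3 |
| 5.8.4 | first admission; recurrent rate | 2 |
| 5.8.5 | cognitive decline | 1 |
| 5.8.6 | 3 PROMIS domains × 3 visits | 9 |
| 5.8.7 | acute GVHD II-IV; III-IV | 2 |
| 5.8.8 | chronic GVHD | 1 |
| 5.8.9 | serious organ toxicity | 1 |
| 5.8.10 | survival after acute GVHD | 1 |
| Total | | 23 |

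Without 5.8.10 the count is 22. Table 4.2.4 does not mark PROMIS physical function at day 365, although sections 2.5 and 3.2.6 and the Appendix 4 table include it. Dropping that as well gives 21. The count leaves out pairwise tertile contrasts, the relapse subgroups for cognition (3.2.5), the individual-predictor models in 5.8.2 and 5.8.3, and the quantitative-score sensitivity analyses.

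**Family-wise error at 1% per test:**

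| Tests k | Bound k × 0.01 | Independent 1 − 0.99^k | Level needed 0.10 / k |
|---|---|---|---|
| 21 | 21% | 19.0% | 0.48% |
| 22 | 22% | 19.8% | 0.45% |
| 23 | 23% | 20.6% | 0.43% |

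The tests are positively correlated because they share subjects, one score, repeated visits and nested GVHD grades. The protocol gives no correlations, so a range was simulated with 23 two-degree-of-freedom tests and 200,000 draws. Examples, as correlation within an endpoint / between endpoints:

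- 0.3 / 0: about 20%
- 0.7 / 0.3: 15.0%
- 0.8 / 0.5: 11.5%
- 0.9 / 0.5: 10.4%

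**NRM share of deaths**, from Table 5.9.2 weighted by the numbers evaluated (its treatment-related mortality is taken as NRM):

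- 1-year NRM: (1537 × 18 + 1761 × 21 + 689 × 26 + 78 × 29) / 4065 = 20.9%
- 1-year survival: (1617 × 63 + 1816 × 61 + 704 × 57 + 81 × 57) / 4218 = 61.0%, so deaths are 39.0%
- Share: 20.9 / 39.0 = 0.54

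**Level of the in-sample overall survival test.** A complete null was simulated: 880 subjects, 13 candidate binary predictors unrelated to any outcome, NRM about 21%, survival about 62%, NRM about 57% of deaths, and 1,500 trials per setting. CHARM was built by stepwise Cox regression on NRM and cut at tertiles. Overall survival was then tested at 1% in the same subjects. A trial in which no variable was selected counted as no rejection.

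| Selection (assumed) | Rejection at nominal 1% |
|---|---|
| p < 0.05 | 5.7 to 6.6% |
| p < 0.10 | 9.3 to 11.7% |

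The ranges are for predictor correlation 0.3 and 0. Assumptions not taken from the protocol are the stepwise threshold, 25% prevalence for the three predictors without a stated frequency, constant hazards, and the relapse and post-relapse death rates. The forced adjustment variables and the cut-point exploration of 5.7.1 were not simulated. The cut-point search would add optimism.

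**The case against.** **The count of ten may be right as a count of endpoints.** The protocol says "since we will be considering 10 endpoints between section 5.8.1 and 5.8.9". If acute GVHD II-IV and III-IV are counted separately, those sections hold exactly ten endpoints, so a reader should not conclude that the authors miscounted nine subsections. This stands. But 5.8.10 is then an eleventh endpoint tested at 1%, and three domains at three visits still count as one.

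**Some comparisons are worded as estimation, and a reduction to one test could sit in the analysis plan.** This is partly fair for mean disability and recurrent admissions. The regression sentence in 5.8.7 also does not say which grade it models; both are counted because the section names both. Yet the protocol did not leave multiplicity open. It fixed the error rate, the divisor and the level for all secondary analyses, and 5.8.6 commits to comparisons at each time point.

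**The excess may be small.** A reader might infer that the true error is 21 to 23%. That is a bound, and 19 to 21% needs independence. With strong correlation the value falls to near 10%, so the documents support only the statement that 10% is not guaranteed.

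**The survival test need not exhaust the budget.** A reader might infer that it alone spends more than the whole 10%. A test of the quantitative score would suggest so (about 12 to 13% at p < 0.05 selection), but that is the sensitivity analysis. For the planned tertile test the figure is about 6% at p < 0.05 and passes 10% only in some settings with looser selection.

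**A complete null is remote.** Table 5.9.1 assumes hazard ratios of 1.1 to 2.3 for 12 of the 13 candidates. If CHARM predicts NRM, much of its association with overall survival will be real. The practical harm is then an inflated hazard ratio and an overstated p-value rather than a wholly false finding. The size of that inflation was not calculated.

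**Conclusion.** Both parts hold. The 1% level is correct arithmetic on a divisor that does not match the analyses listed. With 21 to 23 comparisons, the family-wise error is at most 21 to 23%, is 19 to 21% under independence, and is roughly 10 to 20% over the positive correlations tried.

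The in-sample tests of overall survival and of survival after acute GVHD do not have a valid 1% level. For overall survival, the complete-null rejection rate is about 6 to 12 times nominal, given the assumed selection thresholds and hazards. Survival after acute GVHD was not simulated; it shares the defect because its deaths include NRM deaths used to build the score.

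Severity is moderate. The primary objective, its internal validation and the sample size are untouched.

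**What to change.** Before analysis:

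1. Name one confirmatory CHARM-group test for each of 5.8.1 to 5.8.10 and correct the cited range to end at 5.8.10. For HRQOL, use a joint test over domains and visits; for disability, time to development or progression; for facility admission, time to first admission; for acute GVHD, grade II-IV. That makes ten tests, and 10 × 1% = 10% keeps the sponsor's own figures.
2. Report the remaining comparisons as estimates with confidence intervals and no claim of significance. Alternatively, apply Holm across all of them.
3. For overall survival and survival after acute GVHD, compute each subject's CHARM score from models that did not use that subject (out-of-bag or cross-validated), within the resampling already planned. The whole sequence of variable and cut-point selection must be repeated in each resample. State the stepwise threshold.

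The cost is wording, a little programming and the loss of nominal significance for some comparisons. No new subjects, visits or data are needed.

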A composite health risk score will be constructed from the final Cox model by summing the log hazard ratios for each of the relevant covariates to be included in the scoring system. We will also consider approximating the score by replacing the log hazard ratios with a numeric scoring system for ease of clinical use and will consider the creation of up to 3 groups based on tertiles of this score to facilitate summarizing the effects through cumulative incidence curves by group. The following baseline variables will be kept/forced into the multivariate model during the modeling process: donor type and HLA matching, donor/recipient CMV status and intensity of conditioning regimen. While these baseline variables will be used to adjust the multivariate model, they will not contribute to the scores created for the final CHARM. Specifically, we will only use the linear predictors ($X\beta$ terms) corresponding to the variables from Table 5.9.1 to construct the final CHARM score. Other baseline variables, as mentioned before, will be included in the multivariate regression model to account for additional differences in risk related to transplant or donor matching issues but not used to construct the CHARM score. We anticipate that there will be missing data among the CHARM variables. Therefore, multiple imputation methods may be used before developing the CHARM score.

Although the Cox regression model will be the primary method of analysis, we plan on investigating an alternative secondary prediction model using machine learning techniques such as CoxBoost.⁶¹ CoxBoost utilizes boosting along with a flexible penalization of covariates to build prediction models for survival and competing risks data in a proportional hazards

framework. It can handle potentially high-dimensional and diverse clinical and biomarker covariates. The number of boosting steps and the number of path algorithm steps will be tuned through cross-validation. The original bootstrap is not a particularly good estimator for cross validation. Therefore, we will compare and contrast the prediction performance of the primary and secondary models using 632+ bootstrap cross-validation as detailed below.⁶² The 632+ bootstrap is a weighted average of the leave-one-out bootstrap estimator and the naïve estimate of prediction error using weights 0.632 and 0.368, respectively.

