5.8.2 Development/Progression of Frailty (DPF)

Frailty will be summarized at each time point using descriptive statistics. Incidence of DPF up to 1 year will be estimated with 95% confidence intervals using the cumulative incidence estimate, treating death prior to DPF as a competing event. A multivariate Cox regression model for the cause-specific hazard of DPF will be fit to estimate hazard ratios of the CHARM risks groups after adjustment for baseline characteristics as described above. Additionally, we will develop a separate Cox model using individual predictors rather than the overall CHARM score in order to assess the relative importance of the predictors in Table 5.9.1 on DPF and compare to CHARM predictive power for DPF.

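### Section 5.8 decides the secondary endpoints on CHARM tertile groups and leaves the more efficient test of the quantitative score as a sensitivity analysis

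*Protocol*

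**What the plan says.** Protocol section 5.8 sets the form of the score for all secondary endpoints: "Three risk groups will be formed, based on the tertiles of the CHARM risk score". It also fixes the level: "Assuming an overall type I error of 10%, a significance level of 1% will be used for all secondary analyses based on Bonferroni adjustment". The divisor is the ten endpoints that the section counts in 5.8.1 to 5.8.9. The score in its own scale comes second: "A sensitivity analyses will also be done base on the CHARM score as a quantitative measure rather than tertile groups".

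The endpoint subsections follow the group form. Overall survival (5.8.1) uses a Cox model "to estimate hazard ratios for the CHARM risk groups after adjustment for baseline characteristics as described above". Frailty (5.8.2) uses one "to estimate hazard ratios of the CHARM risks groups after adjustment for baseline characteristics as described above". The remaining subsections, through 5.8.10, also estimate effects of the risk groups or compare them. Quality of life (5.8.6) speaks of "the effect of baseline covariates including the composite health risk score on the health-related QOL outcomes" but ends with adjusted comparisons between the risk groups.

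Section 5.7.1 builds the score differently. It is the sum of the log hazard ratios of the retained Table 5.9.1 variables, that is, their part of the linear predictor. An integer approximation is an option. Tertiles appear there only as a way to summarise effects through cumulative incidence curves: the plan "will consider the creation of up to 3 groups based on tertiles of this score".

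The synopsis states the secondary objective as the association of the composite model with the outcomes, and section 2.2.3 states it as the model's ability to predict them. Section 2.2.1 adds a hypothesis in terms of groups, for quality of life, frailty, nursing-home admission and disability.

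**The concern.** In section 5.7.1 tertiles are a display device. In section 5.8 the same tertiles carry the inference at a strict 1% level. Cutting a linear predictor into three groups treats everyone within a third as equal, so real differences in predicted risk within a group no longer count. If the groups are then tested jointly, the second degree of freedom costs more power.

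At stake is whether the study detects associations between CHARM and the secondary outcomes that its data could show. The better-powered test will be run in any case, but as a sensitivity analysis it cannot carry the conclusion.

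**Working it through.** **Inputs from the protocol.** Overall secondary type I error 10% and 10 endpoints (5.8); three tertile groups (5.8); frequencies and hazard ratios of the candidate predictors (Table 5.9.1). The protocol gives no power, effect size or score distribution for secondary endpoints.

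**Assumptions.** A roughly normal score; a linear effect on the log-hazard, log-odds or mean scale; the adjustment covariates affecting both forms of the score equally; starting power of 80% or 90% for the quantitative test.

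**Step 1: the plan's own figures.** 10% / 10 = 1%, as stated. The other design figures also reproduce. The sample size is 12 × 16 / 0.22 = 872.7, against a planned 880, which gives 880 × 0.22 / 16 = 12.1 events per variable. The detectable hazard ratios in Table 5.5 recompute to 1.962, 1.825, 1.743, 1.691 and 1.634, against the printed 1.96, 1.83, 1.75, 1.69 and 1.63. These last two concern the primary model only.

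**Step 2: loss from grouping.** For a standard normal score the top tertile has mean m = 3φ(z₂⸝₃) = 1.0908, the middle 0 and the bottom −1.0908. The share of variance lying between groups is

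(2/3) × m² = (2/3) × 1.0908² = 0.793.

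High versus low gives the same value, (2m)² / 6 = 0.793, and so does a trend over the three groups. The loss is 1 − 0.793, about 21%.

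**Step 3: cost of the second degree of freedom.** For 80% power at 1%, the noncentrality needed is 11.68 with 1 df and 13.88 with 2 df, a ratio of 0.841. Relative efficiency of the 2-df tertile test is 0.793 × 0.841 = 0.667, a loss of about 33%. At 90% power the noncentralities are 14.88 and 17.43, and the efficiency is 0.677.

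**Step 4: power at one fixed effect.** With 80% power on the score, the tertile noncentrality is 0.793 × 11.68 = 9.26. With 90% it is 0.793 × 14.88 = 11.80. The noncentral chi-square then gives:

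| Test at 1% | Relative efficiency | Score at 80% | Score at 90% |
|---|---|---|---|
| Quantitative score, 1 df | 1 | 80% | 90% |
| High vs low, or tertile trend, 1 df | 0.793 | 68% | 81% |
| Global tertile test, 2 df | 0.667 to 0.677 | 57% | 71% |

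**Step 5: other score shapes.** The grouping loss alone is 11% for a uniform score and 35% for an exponential one. Scores simulated from the Table 5.9.1 frequencies and hazard ratios, with predictors taken as independent, keep these shares:

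- nine items (age, HCT-CI, KPS, physical function, IADL, walk speed, MoCA, CRP, albumin): 0.813
- HCT-CI, IADL, MoCA, CRP, albumin: 0.843
- HCT-CI, MoCA, albumin, walk speed: 0.726
- HCT-CI, IADL, albumin: 0.884

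That is a loss of about 12% to 27%. With few binary items, ties also make the tertiles unequal: the four-item score splits about 65% / 5% / 30%.

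**The case against.** The best defence is that groups match a stated hypothesis. Section 2.2.1 says the score will define groups with different trajectories, and section 5.1 describes trajectories among groups with different scores. This stands in part. The hypothesis covers only some of the outcomes, while the association objective covers all of them; tertile curves and hazard ratios would still serve it if the deciding test used the score.

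Second, the quantitative analysis is already planned, so the dispute is over which analysis leads. That is true, and it is why this is an improvement and not the correction of an error.

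Third, CHARM is weighted for non-relapse mortality, and nothing in the protocol shows a linear effect on quality of life, cognition, GVHD or facility admission. Groups tolerate non-linearity better. This stands as the real cost of the change.

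A reader might also infer more than the text supports:

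- **That leaving the contrast among the three groups unnamed is itself a defect, or leaves the 10% overall error unprotected.** Which contrast is tested can properly be left to a statistical analysis plan, which is not at hand, and the protocol does not say that every pair will be tested.
- **That sections 5.7.1 and 5.8.6 contradict 5.8.** The option of up to three groups in 5.7.1 concerns a display for the primary endpoint, and 5.8.6 ends with the same group comparisons as 5.8.

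**Conclusion.** The concern holds as a matter of efficiency. Section 5.8 puts the weaker of two planned analyses first for an objective about association. Under a normal score and a log-linear effect the loss is about 21% with a single high-versus-low or trend test, and about 33% with a 2-df global test at 1%. The grouping part is about 12% to 27% for scores built from Table 5.9.1.

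A reader might take a third as the general loss. It is not: it belongs to the 2-df test, which the protocol does not name. Nor should the efficiency be turned into a number of the 880 subjects. The protocol states no secondary power, information in the Cox analyses depends on events, and some endpoints use only part of the cohort: survival after acute GVHD needs patients who develop it, and cognitive decline needs a day-100 MoCA. The 80% and 90% starting points are illustrative. Contrasts may fall on different sides of 1% for a borderline endpoint, but that is less than reaching opposite conclusions. No figure stated in the protocol is wrong.

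**What to change.** In section 5.8, name the 1-df test of the quantitative CHARM score as the single deciding test for each secondary endpoint, at the stated 1%. Keep the tertile groups for univariate summaries, curves and hazard ratios with confidence intervals. They then serve the group hypothesis in 2.2.1 and show any marked departure from linearity.

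The cost is an edit to the text, since both analyses are already planned and no new data are needed. The downside is that the deciding test assumes an approximately log-linear effect and can lose power where the effect is strongly non-linear.
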